11.2.10. Sample Retention and Future Biomedical Research

The retention period of laboratory samples will be 15 years, or as permitted by local regulations, to address further scientific questions related to mRNA-1273 or anti-respiratory virus immune response. In addition, identifiable samples can be destroyed at any time at the request of the participant. During the study, or during the retention period, in addition to the analysis outlined in the study endpoints, exploratory analysis may be conducted, using other Ab-based methodologies, on any remaining blood or serum samples, including participants who provide samples for screening, but are not subsequently enrolled. These analyses would extend the search for other potentially relevant biomarkers to investigate the effect of mRNA-1273, as well as to determine how changes in the markers may relate to exposure and clinical outcomes. A decision to perform such exploratory research may arise from new scientific findings related to the drug class or disease, as well as reagent and assay availability.

11.2.11. Data Quality Assurance and Quality Control

Data collection is the responsibility of the clinical study staff at the site under the supervision of the site investigator. The investigator is responsible for ensuring the accuracy, completeness, legibility, and timeliness of the data reported.

- All participant data relating to the study will be recorded eCRF unless transmitted to the Sponsor or designee electronically (eg, laboratory data). The investigator is responsible for verifying that data entries are accurate and correct by physically or electronically signing the eCRF.
- The investigator must maintain accurate documentation (source data) that supports the information entered in the eCRF.
- The investigator must permit study-related monitoring, audits, IRB/IEC review, and regulatory agency inspections and provide direct access to source data documents.
- Monitoring details describing strategy (eg, risk-based initiatives in operations and quality such as Risk Management and Mitigation Strategies and Analytical Risk-Based Monitoring), methods, responsibilities and requirements, including handling of noncompliance issues and monitoring techniques (central, remote, or on-site monitoring) are provided in the study Monitoring Plan, Centralized Monitoring Plan, and Risk Management Plan.
- The Sponsor or designee is responsible for the data management of this study including quality checking of the data.
- The Sponsor assumes accountability for actions delegated to other individuals (eg, CROs).
- Study monitors will perform ongoing source data verification to confirm that data entered into the eCRF by authorized site personnel are accurate, complete, and verifiable from source documents; that the safety and rights of participants are being protected; and that the study is being conducted in accordance with the currently approved protocol and any other study agreements, ICH GCP, and all applicable regulatory requirements.
- Records and documents, including signed ICFs, pertaining to the conduct of this study must be retained by the investigator for 15 years after study completion unless local regulations or institutional policies require a longer retention period. No records may be destroyed during the retention period without the written approval of the Sponsor. No records may be transferred to another location or party without written notification to the Sponsor.

Quality assurance (QA) includes all the planned and systematic actions that are established to ensure that the clinical study is performed, and the data are generated, documented (recorded), and reported according to ICH GCP and local/regional regulatory standards.

A QA representative from the Sponsor or qualified designee, who is independent of and separated from routine monitoring, may periodically arrange inspections/audits of the clinical study by reviewing the data obtained and procedural aspects. These inspections may include on-site inspections/audits and source data checks. Direct access to source documents is required for the purpose of these periodic inspections/audits.

11.2.12. Data Collection and Management

This study will be conducted in compliance with ICH CGP guidelines. This study will also be conducted in accordance with the most recent version of the Declaration of Helsinki.

This study will use electronic data collection (to collect data directly from the investigational site using eCRFs). The investigator is responsible for ensuring that all sections of each eCRF are completed promptly and correctly and that entries can be verified against any source data.

Study monitors will perform source document verification to identify inconsistencies between the eCRFs and source documents. Discrepancies will be resolved in accordance with the principles of GCP. Detailed study monitoring procedures are provided in the Clinical Monitoring Plan.

AEs will be coded with the most current available version of MedDRA. Concomitant medications will be coded using WHO – Drug Reference List.

11.2.13. Source Documents

Source documents are original documents or certified copies, and include, but are not limited to, diaries, medical and hospital records, screening logs, informed consent/assent forms, telephone contact logs, and worksheets. Source documents provide evidence for the existence of the participant and substantiate the integrity of the data collected. Source documents are filed at the investigator's site.

Data reported on the CRF or entered in the eCRF that are transcribed from source documents must be consistent with the source documents or the discrepancies must be explained. The investigator may need to request previous medical records or transfer records, depending on the study. Also, current medical records must be available.

Moderna or its designee requires that the investigator prepare and maintain adequate and accurate records for each participant treated with the IP. Source documents such as any hospital, clinic, or office charts and the signed ICFs are to be included in the investigator's files with the participant's study records.

11.2.14. Retention of Records

The Principal Investigator must maintain all documentation relating to the study for a period of at least 2 years after the last marketing application approval or, if not approved, 2 years following the discontinuance of the test article for investigation. If this requirement differs from any local regulations, the local regulations will take precedence unless the local retention policy is less than 2 years.

If it becomes necessary for Moderna or the regulatory authority to review any documentation relating to the study, the investigator must permit access to such records. No records will be destroyed without the written consent of the Sponsor, if applicable. It is the responsibility of the Sponsor to inform the investigator when these documents no longer need to be retained.

11.2.15. Study and Site Closure

If the study is prematurely terminated or suspended, the Sponsor shall promptly inform the investigators, the IECs/IRBs, the regulatory authorities, and any CRO(s) used in the study of the reason for termination or suspension, as specified by the applicable regulatory requirements. The investigator shall promptly inform the participant and should assure appropriate participant therapy and/or follow-up.

The Sponsor or designee reserves the right to close the study site or terminate the study at any time for any reason at the sole discretion of the Sponsor.

The investigator may initiate study-site closure at any time, provided there is reasonable cause and sufficient notice is given in advance of the intended termination.

Reasons for the early closure of a study site by the Sponsor or investigator may include but are not limited to:

- Continuation of the study represents a significant medical risk to participants.
- Failure of the investigator to comply with the protocol, the requirements of the IRB/IEC or local health authorities, the Sponsor's procedures, or GCP guidelines.
- Inadequate recruitment of participants by the investigator.
- Discontinuation of further mRNA-1273 development.

Study sites will be closed upon study completion. A study site is considered closed when all required documents and study supplies have been collected and a study-site closure visit has been performed.

11.2.16. Publication Policy

The results of this study may be published or presented at scientific meetings. If this is foreseen, the investigator agrees to submit all manuscripts or abstracts to the Sponsor before submission. This allows the Sponsor to protect proprietary information and to provide comments.

The Sponsor will comply with the requirements for publication of study results. In accordance with standard editorial and ethical practice, the Sponsor will generally support publication of multicenter studies only in their entirety and not as individual site data. In this case, a coordinating investigator will be designated by mutual agreement.

Authorship will be determined by mutual agreement and in line with International Committee of Medical Journal Editors authorship requirements.

The clinical study plan and the results of the study will be published on www.ClinicalTrials.gov in accordance with 21 CFR 50.25(c). The results of and data from this study belong to Moderna.

11.3. APPENDIX 3: Contraceptive Guidance

Woman of Childbearing Potential (WOCBP)

Females of childbearing potential are those who are considered fertile following menarche and until becoming postmenopausal unless permanently sterile (see below). If fertility is unclear (eg, amenorrhea in adolescents or athletes) and a menstrual cycle cannot be confirmed before first dose of study treatment, additional evaluation should be considered.

Women in the following categories are not considered WOCBP:

1. Premenarchal
2. Premenopausal, surgically sterile female with 1 of the following:
 - a. Documented complete hysterectomy
 - b. Documented bilateral salpingectomy
 - c. Documented bilateral oophorectomy

For individuals with permanent infertility due to an alternate medical cause other than the above, (eg, mullerian agenesis, androgen insensitivity), investigator discretion should be applied in determining study entry.

Note: Documentation can come from the site personnel's: review of the participant's medical records, medical examination, or medical history interview.

3. Postmenopausal female
 - A postmenopausal state is defined as no menses for 12 months without an alternative medical cause. The following age-specific requirements apply:
 - Women < 50 years of age would be considered postmenopausal if they have been amenorrheic for 12 months or more following cessation of exogenous hormonal treatments and if they have luteinizing hormone and FSH levels in the postmenopausal range for the institution.
 - Women ≥ 50 years of age would be considered postmenopausal if they have been amenorrheic for 12 months or more, had radiation-induced menopause with last menses > 1 year ago or had chemotherapy-induced menopause with last menses > 1 year ago.
 - A high FSH level in the postmenopausal range may be used to confirm a postmenopausal state in women not using hormonal replacement therapy (HRT).
 - Females on HRT and whose menopausal status is in doubt will be required to use one of the non-estrogen hormonal highly effective contraception methods if they wish to

continue their HRT during the study. Otherwise, they must discontinue HRT to allow confirmation of postmenopausal status before study enrollment.

11.4. APPENDIX 4: Statistical Appendices

11.4.1. Estimands and Estimand Specifications

Table 24: Intercurrent Event Types

Label	Intercurrent Event Type	Comment
IcEv1 (death without confirmation of cases, ie, unrelated death)	Unrelated death without documented confirmed COVID-19	Participants in PP Set who die due to reasons unrelated to COVID-19 without confirmation of being a case will all be included in statistical analysis.
IcEv2 (early COVID-19)	COVID-19 starting up to 14 days after the second dose of IP	Participants in PP Set who experience early COVID-19 up to 14 days after the second dose of IP will all be included in statistical analysis.

Abbreviations: COVID-19 = coronavirus disease 2019; IcEv: intercurrent event; IP = investigational product; PP: per-protocol.

Table 25: Primary Objective and Estimands With Rationale for Strategies to Address Intercurrent Events for Per-protocol Analysis

Objective: To demonstrate the efficacy of mRNA-1273 to prevent COVID-19	
Estimand Description	Vaccine efficacy will be measured using 1 – HR (mRNA-1273/placebo) of COVID-19 from 14 days after second dose of IP in adults. A hypothetical strategy will be used for deaths unrelated to COVID-19, and a hypothetical strategy will also be used for early COVID-19 in participants in the PP Set.
Target Population	Adults aged 18 years and older in circumstances at a high risk of SARS-CoV-2 infection but without medical conditions that pose additional risk of developing severe disease. The population excludes those previously infected or vaccinated for SARS-CoV-2 or with a medical condition, on treatment that poses additional risks (including those requiring immunosuppressants or immune-modifying drugs), or SARS-CoV-2 pre-positive.
Variable/Endpoint	Time to COVID-19 disease, censoring at early discontinuation, early COVID-19, or last assessment for an event not being observed, whichever comes earlier.
Treatment Condition(s)	Test: mRNA-1273 Reference: Placebo
Estimand Label	Estimand 1
Population-Level Summary	Vaccine efficacy defined as 1 - HR of mRNA-1273/placebo
Intercurrent Event Strategy	
IcEv1 (Unrelated death):	Hypothetical
IcEv2 (early infection):	Hypothetical
Rationale for Strategy(s)	Hypothetical: unrelated death without confirmation of COVID-19 will be censored at the time of death as if there is no event, handled with independent censoring. Hypothetical: early case in PP Set will be censored at the time of case onset if it is not a case, handled with independent censoring.

Abbreviations: COVID-19 = coronavirus disease 2019; HR = hazard ratio; IcEv = intercurrent event; IP = investigational product; PP = per protocol; SARS-CoV-2 = severe acute respiratory syndrome coronavirus 2.

11.4.2. Statistical Methods and Sensitivity Analyses

Table 26: Summary of Statistical Methods and Sensitivity Analyses

Estimand Label	Estimand Description	Main Estimation			Sensitivity Analysis
		Analysis Set	Imputation/Data/Censoring Rules	Analysis Model/Method	
Estimand 1	See Table 25	PP Set	
Participants who did not develop COVID-19, ongoing or complete the study will be censored at the last assessment.
 
Participants who discontinue early or die without COVID-19 will be censored at the date of discontinuation or death, respectively.
 
Participant who is a confirmed case prior to 14 days after the second dose of IP will be censored on the date of confirmation.
	
The (1 - HR) with 95% CI will be estimated using Cox proportional hazard regression analysis with treatment arm as a fixed effect stratified by randomization stratification factors. And the null hypothesis will be tested using Wald Chi-square method.
	
As described in Section 9.5.1 with cases counted starting after the second dose of IP.

Abbreviations: CI = confidence interval; COVID-19 = coronavirus disease 2019; HR = hazard ratio; IP = investigational product; PP = per protocol.

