9.3. Sample Size Determination

The sample size is driven by the total number of cases to demonstrate VE (mRNA-1273 vs. placebo) to prevent COVID-19 in Part A. Under the assumption of proportional hazards over time and with 1:1 randomization of mRNA-1273 and placebo, a total of 151 COVID-19 cases will provide 90% power to detect a 60% reduction in hazard rate (60% VE), rejecting the null hypothesis H_0 : VE $\leq 30\%$, with 2 IAs at 35% and 70% of the target total number of cases using a 1-sided O'Brien-Fleming boundary for efficacy and a log-rank test statistic with a 1-sided false positive error rate of 0.025. The total number of cases pertains to the PP Set accruing at least 14 days after the second dose. There are 2 planned IAs in this study, which will be performed when approximately 35% and 70% of the target total number of cases have been observed. Approximately 30,000 participants will be randomized with the following assumptions:

- The target VE against COVID-19 is 60% (with 95% CI lower bound ruling out 30%, rejecting the null hypothesis H_0 : VE $\leq 30\%$)
- A 6-month COVID-19 incidence rate of 0.75% in the placebo arm
- An annual dropout rate of 2% (loss of evaluable participants)
- Two IAs at 35% and 70% of total target cases across the 2 treatment groups with O'Brien-Fleming boundaries for efficacy monitoring
- 3-month uniform accrual
- Approximately 15% of participants will be excluded from the PP population, and participants are at risk for COVID-19 starting 14 days after the second dose

[Table 6](#) provides sample size with 90% power to demonstrate VE on COVID-19.

Table 6: Conditions and Sample Size to Demonstrate Vaccine Efficacy

Target VE	Lower Bound	Randomization Ratio	Total # of Cases	6-Month Incidence Rate		Total Sample Size ^a
				Placebo	mRNA-1273	
--	--	--	--			--
60%	30%	1:1	151	0.75%	0.30%	30,000

Abbreviations: IP = investigational product; PP = Per Protocol; VE = vaccine efficacy.

[figure not shown]
^a Sample size to account for 15% participants to be excluded from the PP Set (eg, seropositive at baseline, have not received planned IP).

The sample size is calculated using R package gsDesign ([Anderson 2020](#)).

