9.5.1.1. Efficacy Analysis on Primary Endpoint

To assess the primary efficacy endpoint of VE of mRNA-1273 in preventing the first occurrence of COVID-19 from 14 days after second dose of IP, Cox proportional hazards regression will be used to estimate proportional hazards VE (PH VE), measured by one minus the HR (mRNA-1273 vs. placebo), with a 2-sided score-based 95% CI and 2-sided p-value for testing $H_0: VE \leq 30\%$.

Vaccine efficacy is defined as the percent reduction in the hazard of the primary endpoint (mRNA-1273 vs. placebo). The VE will be estimated using one minus the HR (mRNA-1273 vs. placebo) estimand. A stratified Cox proportional hazard model will be used to assess the magnitude of the treatment group difference (ie, HR) between mRNA-1273 and placebo. The HR and its 95% CI from the stratified Cox model with Efron's method of tie handling and with treatment group as covariate will be reported. The same stratification factors used for randomization will be applied to the stratified Cox model.

For the primary efficacy endpoints, participants without documented COVID-19 will be censored at the last study assessment date. Potential intercurrent events may include: 1) death unrelated to COVID-19 and 2) early COVID-19 up to 14 days after second study dose.

In the estimand of the primary analysis on the primary endpoint, a hypothetical strategy will be used for death unrelated to COVID-19; a hypothetical strategy will also be used for early COVID-19, where the time to COVID-19 will be censored at the onset day of early case. The details of intercurrent event description and estimand strategies are presented in [Section 11.4.1](#).

For the primary efficacy analysis, cases will be counted starting 14 days after the second vaccination. Sensitivity analyses with cases counted immediately after the second vaccination, and after randomization will also be carried out.

Analyses of the primary endpoint will be also performed based on the mITT Set using the same methods described above.

For the primary efficacy analysis, cases will be counted starting 14 days after the second dose of IP. Sensitivity analyses with cases counted starting immediately after the second dose of IP and starting immediately after randomization will also be carried out.

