9.5.1.2. Efficacy Analysis on Secondary Endpoint

For each of the below secondary objectives:

- Vaccine efficacy to prevent severe COVID-19
- Vaccine efficacy to prevent serologically confirmed SARS-CoV-2 infection or COVID-19 regardless of symptomatology or severity
- Vaccine efficacy to prevent COVID-19 using a broad definition of symptoms
- Vaccine efficacy to prevent death caused by COVID-19
- Vaccine efficacy to prevent asymptomatic SARS-CoV-2 infection

For each of the above secondary objectives, the same Cox proportional hazard model described above for the primary objective will be applied using the PP Set, with cases counted starting 14 days after the second dose of IP. Sensitivity analyses with cases counted starting after the second dose of IP, 14 days after the first dose of IP, after the first dose of IP, and after randomization will also be performed.

The same model will be applied using the mITT population with cases counted starting 14 days after the second dose of IP.

Vaccine efficacy will be estimated with 1- ratio of incidence rates with the 95% CI using the exact method conditional upon the total number of cases.

Vaccine efficacy to prevent COVID-19 after the first dose of IP

The same Cox proportional hazard model described above for the primary objective will be applied using the PP Set, with cases counted starting 14 days after the first dose of IP.

Vaccine efficacy to prevent COVID-19 regardless of prior SARS-CoV-2 infection

The FAS will be used for analysis to evaluate VE to prevent COVID-19 regardless of prior SARS-CoV-2 infection. The same methods described above for the primary objective will be applied with cases counted starting 14 days after the second dose of IP. Sensitivity analyses with cases counted starting after the second dose of IP, 14 days after the first dose of IP, the first dose of IP, and randomization will also be performed.

Vaccine efficacy will be estimated with $1 - \text{ratio of incidence rates}$ with the 95% CI using the exact method conditional upon the total number of cases.

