In addition to the information presented in the statistical analysis plan section of the protocol (Section 9) which provides the principal features of analyses for this study, this SAP provides statistical analysis details/data derivations. It also documents modifications or additions to the analysis plan which are not “principal” in nature and result from information that was not available at the time of protocol finalization.

Study mRNA-1273-P301 is a Phase 3, randomized, stratified, observer-blind, placebo-controlled study to evaluate the efficacy, safety, and immunogenicity of messenger ribonucleic acid (mRNA)-1273 SARS-CoV-2 vaccine compared to placebo in adults 18 years of age and older who have no known history of SARS-CoV-2 infection but whose locations or circumstances put them at appreciable risk of acquiring COVID-19 and/or SARS-CoV-2 infection.

PPD Biostatistics and programming team, designee of Moderna Biostatistics and Programming department, will perform the statistical analysis; Statistical Analysis System (SAS) Version 9.4 or higher will be used, and R or RStudio may be used. SAP version 1.0, dated 08-September-2020 was finalized and approved prior to the first interim analysis clinical database lock and treatment unblinding for the study. If the methods in this SAP differ from the methods described in the protocol, the SAP will prevail.

In this document, subject and participant are used interchangeably; injection of IP, injection, and dose are used interchangeably; vaccination group and treatment group are used interchangeably.

2. Study Objectives

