6.3.1.2. Primary Analysis Approach

The number and percentage of subjects who had an event (i.e. the first occurrence of COVID-19 starting 14 days after the second injection, date of documented COVID-19 – date of the second injection ≥ 14) and subjects who were censored will be summarized.

The non-parametric Kaplan-Meier method will be used to estimate the time to first occurrence of COVID-19 curve in each treatment group.

Vaccine efficacy (VE) is defined as the percent reduction in the hazard of the primary endpoint (mRNA-1273 vs. placebo), i.e. one minus the hazard ratio (HR). The null hypothesis is:

$$H_0^{\text{efficacy}}: \text{vaccine efficacy} \leq 0.3$$

Equivalently, the null hypothesis is:

$$H_0^{\text{efficacy}}: \text{hazard ratio (HR)} \geq 0.7$$

A stratified Cox proportional hazard (PH) model with Efron's method of tie handling and with treatment group as covariate will be used to assess the magnitude of the treatment group difference (i.e. HR) between mRNA-1273 vs. placebo. The same stratification

factors used for randomization ([Section 4.4](#)) will be applied to the stratified Cox model. VE with corresponding alpha-adjusted confidence interval (CI), 95% CI, and one-sided p -value for testing the null hypothesis from the stratified Cox model would be reported at a planned interim analysis up to the analysis at which vaccine efficacy is demonstrated. After vaccine efficacy was demonstrated, VE and 95% CI would be provided for subsequent analysis/updates of efficacy.

In this study, vaccine efficacy was demonstrated based on pre-specified statistical criterion (Section 6.4) at the first interim analysis, at which, one-sided p -value for testing the null hypothesis of $VE \leq 0.3$, 95% CI and alpha-adjusted CI were provided from the stratified Cox model. At the primary analysis where the total number of COVID-19 cases > 151 , total target number of cases, VE, one-sided p -value for testing the null hypothesis of $VE \leq 0.3$ and 95% CI were provided. In subsequent analysis/updates of efficacy, VE and 95% CI will be provided.

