6.3.2.2. Analysis of the secondary efficacy endpoints

Similar analysis methods as for the primary efficacy endpoint will be applied to the following secondary efficacy endpoints based on the PP set, unless otherwise specified:

- VE to prevent severe COVID-19
- VE to prevent serologically confirmed SARS-CoV-2 infection or COVID-19 regardless of symptomatology or severity.

- VE to prevent COVID-19 using a secondary definition of symptoms
- VE to prevent death caused by COVID-19

For each of the above secondary objectives, the following analyses will be performed:

- Primary analysis: VE will be estimated with $1 - HR$ (mRNA-1273 vs. placebo) using a Cox PH model based on the PP Set as described for the primary efficacy endpoint. Kaplan-Meier curves of time to event will be presented for each treatment group.

Cases will be counted starting 14 days after the second injection of IP.

- Analysis using the same model based on the mITT Set as described for the primary efficacy endpoint. Kaplan-Meier curves of time to event will be presented for each treatment group.
- Sensitivity analyses with cases counted starting immediately after the second injection of IP (onset date \geq date of dose 2, considering positive RT-PCR at Day 29), starting 14 days (\geq 14 days) after the first injection of IP, and immediately after randomization respectively.
- VE and 95% CI based on the incidence will be estimated with $1 - \text{ratio of incidence rates}$ using the exact method conditional upon the total number of cases.

For the secondary efficacy objective: VE to prevent asymptomatic SARS-CoV-2 infection

As diseased cases (COVID-19 or secondary definition of COVID-19) are competing events for asymptomatic SARS-CoV-2 infections, competing risk method will be used to estimate the vaccine efficacy of mRNA-1273, specifically, Fine and Gray's (FG) sub-distribution hazard model will be used. Competing risk method will also be used to estimate the cumulative incidence function and the cumulative incidence of asymptomatic SARS-CoV-2 infections will be plotted.

In the primary approach with cases of asymptomatic SARS-CoV-2 infection counted starting 14 days after the second injection, only seroconversion at Day 57 or later will be considered.

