All hypothesis tests against the above three secondary efficacy endpoints will be first against a $VE \leq 0\%$ null hypothesis. If hypothesis test against $VE \leq 0\%$ are rejected for all three, sequential testing against a $VE \leq 10\%$ for these three secondary efficacy endpoints will be performed in the same order; if hypothesis test against $VE \leq 10\%$ are rejected for all three, sequential testing against a $VE \leq 20\%$ for these three secondary efficacy endpoints will be performed in the same order; if hypothesis test against $VE \leq 20\%$ are rejected for all three, sequential testing against a $VE \leq 30\%$ for these three secondary efficacy endpoints will be performed in the same order. No further testing will be performed once the sequence breaks, that is, further testing stops as soon as an endpoint in the sequence fails to show significance against corresponding null hypothesis.

No further testing will be performed once the sequence breaks, that is, further testing stops as soon as an endpoint in the sequence fails to show significance against corresponding null hypothesis regarding VE.

While achieving vaccine efficacy that rules out a lower bound of 30% against COVID-19 is the goal of the study, there is utility in formally assessing VEs that are less than 30%. Therefore, in the situation that the primary efficacy endpoint (VE against COVID-19) does not achieve statistical significance against a $VE \leq 30\%$ null hypothesis at neither the interim analyses nor the primary analysis, at the primary analysis, sequential testing against a $VE \leq 20\%$, a $VE \leq 10\%$, and a $VE \leq 0\%$ will be performed, halting when a rejection occurs. Figure 2 below demonstrates the testing strategy in this study:

Figure 2: Testing Strategy of Primary and Secondary Efficacy Endpoints

At the first interim analysis where vaccine efficacy for COVID-19 has been demonstrated at the pre-specified statistical criterion, there were 11 total severe COVID-19 cases based on adjudication committee starting 14 days after the 2nd injection.

At the time of IA1 and the primary analysis of efficacy, data for secondary efficacy endpoint infection regardless of symptomatology or severity were not available and were not included in these analyses.

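### Protocol Table 26 names a Wald test that cannot reject with no vaccine-arm cases, it conflicts with the score-based interval in Section 9.5.1.1, and the SAP does not say which statistic governs

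*Protocol*

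**What the plan says.** On the primary test:

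- Protocol Section 11.4.2, Table 26, in the row for Estimand 1 (the primary endpoint): "And the null hypothesis will be tested using Wald Chi-square method".
- Protocol Section 9.5.1.1, for the same analysis, plans Cox regression "with a 2-sided score-based 95% CI and 2-sided p-value for testing" the null of VE at most 30%.
- Protocol Section 9.3 derives the 151 cases from "a log-rank test statistic with a 1-sided false positive error rate of 0.025".
- Part A SAP Section 6.3.1.2 plans a one-sided p-value "for testing the null hypothesis from the stratified Cox model would be reported". It does not say whether this is the Wald, score or likelihood-ratio p-value.
- Part A SAP Section 1 sets the precedence: "If the methods in this SAP differ from the methods described in the protocol, the SAP will prevail".

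On the secondary tests:

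- Protocol Section 9.5.1.2: "the same Cox proportional hazard model described above for the primary objective will be applied using the PP Set".
- Part A SAP Section 6.3.2.2: "Similar analysis methods as for the primary efficacy endpoint will be applied to the following secondary efficacy endpoints based on the PP set".
- Part A SAP Section 6.5 tests three secondary endpoints in a fixed order at one-sided 0.025, first against VE ≤ 0%, then 10%, 20% and 30%. Severe COVID-19 is third in each round and is tested at an analysis with at least 20 cases, otherwise at the end of the study. The rule is that "further testing stops as soon as an endpoint in the sequence fails to show significance against corresponding null hypothesis".

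Neither document says what to do if one arm has no cases. The exact method conditional on the case total is planned for a VE estimate and interval (Part A SAP Sections 6.3.1.5 and 6.3.2.2), but it is not assigned to the hypothesis test.

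**The concern.** The documents give one hypothesis two incompatible test procedures, and the SAP does not choose between them. The choice matters because the two part company when the vaccine works very well. With no vaccine-arm cases, the Cox estimate of the log hazard ratio runs to minus infinity and its standard error grows faster still, so the Wald statistic collapses to zero. A score test and an exact test both treat the same data as very strong evidence.

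The place where this could decide a claim is severe COVID-19. It is a confirmatory step with few cases, and Part A SAP Section 6.5 reports only 11 severe cases in total at the first interim analysis. If the Wald test governs there, a zero vaccine-arm count is a failure. That failure removes the severe COVID-19 claim and blocks the VE ≤ 10%, 20% and 30% rounds for all three secondary endpoints.

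**Working it through.** **The plan's own figures.** Table 7, 30 severe cases, true VE 60%: power = Φ(|ln(HR/HR0)|·√30/2 − 1.96).

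- VE ≤ 0%: 0.9163 × 2.7386 − 1.96 = 0.549, giving 70.9% (stated 70.90%).
- VE ≤ 10%: 0.8109 × 2.7386 − 1.96 = 0.261, giving 60.3% (stated 60.30%).
- VE ≤ 20%: 0.6931 × 2.7386 − 1.96 = −0.062, giving 47.5% (stated 47.50%).

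The 151 cases reproduce with separate null and alternative variances of the log hazard ratio. The vaccine share of cases is 0.7/1.7 = 0.4118 under the null and 0.4/1.4 = 0.2857 under the alternative. The variances per case, 1/[p(1 − p)], are 4.129 and 4.900. Then [(1.96 × 2.032 + 1.2816 × 2.214)/0.5596]² = 148.5, and the group-sequential inflation of 1.014 gives 150.6, or 151. Table 7 stops at a true VE of 80%, where zero of 30 has probability 0.4%, so it could not have shown the problem.

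**No vaccine-arm cases, 20 severe cases.** In a stratified Cox fit the estimate diverges: −11.2 (SE 61) at iteration 10 and −21.2 (SE 8988) at iteration 20. The one-sided Wald p-value moves from 0.43 to 0.499 for every null from 0% to 30%. With p0 = HR0/(1 + HR0), the score statistic is (0 − 20p0)/√[20p0(1 − p0)] and the exact p-value is (1 − p0)^20.

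| Null | Score p | Exact p |
|---|---|---|
| VE ≤ 0% | 3.9e-6 | 9.5e-7 |
| VE ≤ 10% | 1.1e-5 | 2.7e-6 |
| VE ≤ 20% | 3.2e-5 | 7.8e-6 |
| VE ≤ 30% | 9.1e-5 | 2.5e-5 |

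**One vaccine-arm case, 20 severe cases.** Wald z = [ln(1/19) − ln HR0]/√(1 + 1/19). Against VE ≤ 30% this is (−2.944 + 0.357)/1.026 = −2.52, p = 0.0058. Against 0%, 10% and 20%, p = 0.0021, 0.0028 and 0.0040. All four nulls are rejected at 0.025.

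**Which counts reject VE ≤ 0% with 20 cases.** At 5 vaccine-arm cases the Wald z is −1.0986/0.5164 = −2.13 (rejects). At 6 it is −0.8473/0.4880 = −1.74 (does not). Wald rejects for 1 to 5 cases, and score and exact reject for 0 to 5. The power lost by Wald is therefore the probability of a zero count, (1 − p1)^n with p1 = (1 − VE)/(2 − VE). At VE 95%, p1 = 0.05/1.05 = 0.0476 and 0.9524^20 = 37.7%. True VE is an assumption, shown as a range:

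| True VE | P(0 of 20) | Wald power, 20 cases | Score or exact power, 20 cases | P(0 of 30) | P(0 of 60) |
|---|---|---|---|---|---|
| 80% | 2.6% | 87.2% | 89.8% | 0.4% | <0.1% |
| 90% | 14.9% | 84.4% | 99.3% | 5.7% | 0.3% |
| 95% | 37.7% | 62.3% | 99.97% | 23.1% | 5.4% |
| 98% | 67.3% | 32.7% | about 100% | 55.2% | 30.5% |

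Over this range Wald power falls as efficacy rises.

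**Primary endpoint.** At the planned 53-case first look, a zero count has probability (1/1.05)^53 = 7.5% at VE 95%. The look actually took place at 95 cases with nominal alpha 0.0047 and p < 0.0001. From the reported VE of 94.5% (86.5 to 97.8), ln HR = −2.900 and SE = [ln 0.135 − ln 0.022]/3.92 = 0.463. Against HR 0.7, z = (−2.900 + 0.357)/0.463 = −5.5, so a Wald test rejects too.

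**The case against.** The strongest reply is that Wald is not shown to be the governing test. The sentence stands once, in an appendix row for the primary estimand. Protocol Section 9.2 and Part A SAP Section 4.2 define primary success by the interval excluding 30%, and Section 9.5.1.1 makes that interval score-based. The log-rank test of Section 9.3 is itself a score test, so the conflict is one table cell against the body of the protocol, not three rival statistics. This stands as to scope. It does not settle the matter: the SAP prevails only where it differs, and since it names no statistic it does not displace the one explicit sentence about the test.

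The second reply is that no text says severe COVID-19 is tested by Wald. The secondary sections carry over a model and similar methods, not a test statistic. This also stands, and the severe COVID-19 consequence is therefore conditional.

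A reader might infer that a near-perfect vaccine would fail the severe COVID-19 step and bring down the whole testing sequence. The documents do not support that. Failure needs exactly zero vaccine-arm cases, and a single case is enough for Wald to reject all four nulls. Section 6.5 sets a floor of 20 severe cases, and a zero count becomes less likely with more. Severe COVID-19 is last in each round, so the primary result and the two earlier VE ≤ 0% rejections would remain.

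Finally, the Part B and C SAP (Section 1) describes the Part A analyses as completed, so a change of deciding test now would be post hoc. That limits the practical effect, but it does not tell a reader which statistic was used.

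**Conclusion.** The point holds as a conflict in the protocol that the SAP leaves open. Table 26 prescribes a Wald test, Sections 9.3 and 9.5.1.1 rest on score methods, and the Wald test gives a wrong non-rejection when the vaccine arm has no cases.

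For severe COVID-19 the size depends on Wald carrying over by inference, on the case total and on true efficacy. With 20 cases the loss of power against VE ≤ 0% is about 15 percentage points at VE 90%, 38 at 95% and 67 at 98%. With 60 cases it is 0.3, 5.4 and 30.5 points. These figures assume equal person-time in the two arms, condition on the case total and ignore the strata. The documents give no split by arm of the 11 severe cases at the first interim analysis, and none is assumed.

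The primary conclusion is not in doubt, since the reported interval excludes 30% by a wide margin under either test.

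**What to change.** Delete the Wald sentence from Protocol Table 26. In Part A SAP Section 6.3.1.2, name the one-sided stratified score (log-rank type) test at the null hazard ratio, with the matching score-based interval, and refer to it from Sections 6.3.2.2 and 6.5 so that it covers the primary and the three sequential secondary tests. For a null of 0.7 the score test needs only a fixed offset of ln 0.7 = −0.357 for the vaccine arm. It behaves properly at zero cases, so no separate zero-case rule is needed. The exact conditional analysis can stay supportive. Death from COVID-19 is outside the confirmatory sequence and needs no deciding test.

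Because the Part A analyses are described as completed, also state which statistic produced the reported p-values and intervals for the primary endpoint and the sequential secondary endpoints. This records what was done; it does not replace the deciding test after the event.

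The cost is wording in one protocol table and three SAP sections, plus a check of the programs already run. Sample size, data collection and interim boundaries do not change.
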